## **Objectives**

This study will investigate the effects of a structured, supervised, home-based combined exercise intervention with self-selected intensity on the chemotherapy completion rates of women with BC. We also intend to analyze the impact of this intervention on functional performance, body composition, PA levels, and quality of life. A 3-month follow-up will be performed to investigate short-term outcomes and active lifestyle sustainability post-intervention.

Hypothesis 1: Women in the intervention will have a better completion rate than those in the control group.

Hypothesis 2: Women in the intervention will present better functional performance, body composition, PA levels, and quality of life than the control group.

Hypothesis 3: In the post-intervention period, women in the intervention group will maintain a more physically active lifestyle than women in the control group.

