### **Sample size**

Considering this study design, sample size calculations were made for the primary outcome with a factorial variance analysis with repeated measures as reference statistical analysis, giving an initial estimation of 82 participants. Based on previous findings and considering a 20% dropout, the sample size was estimated at 98 participants with a moderate effect size ( $\alpha=0.05$ ; statistical power=0.80) according to Cohen's D calculations, using G\* Power 3.1 .

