### **Primary outcome**

**Chemotherapy completion rates.** Chemotherapy completion rates will be assessed at  $T_0$ ,  $T_1$ , and  $T_2$ . This outcome will be reported as the mean RDI ( $\text{mg} \cdot \text{m}^{-2} / \text{wk}^{-1}$ ), which corresponds to a fraction of the planned chemotherapy dose intensity, by dividing the dose of chemotherapy per square meter (of surface area where the drug is related) in each cycle by the number of weeks in a cycle . Information regarding the planned chemotherapy treatment and the effectively received treatment (i.e., dose, type, and duration) will be acquired from medical records after signing the informed consent . A successful chemotherapy completion rate will be considered if the RDI is  $\geq 85\%$  of the planned treatment, as an RDI below this cut-off is associated with a worse disease prognosis and lower treatment efficacy . Calculations to compare the actual chemotherapy dose intensity received and the initially planned dose intensity will be calculated as total milligrams of chemotherapy divided by the product of the body surface (in square meters) and total weeks of treatment . The RDI results from the actual dose intensity received are divided by the planned dose intensity .

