### **Statistical methods**

All data will be analyzed using IBM SPSS (version 29.0). Factorial ANCOVAs with repeated measures will be used for the primary and secondary outcomes, adjusted for potential covariates (e.g., concomitant treatments, BC diagnosis, neo-adjuvant/adjuvant chemotherapy). Independent sample T-tests will be used to compare results between groups at each time point, considering chemotherapy completers versus non-completers . A Fisher's exact test will compare the proportion of participants who needed chemotherapy adjustments from those who did not . The intention-to-treat analysis will be conducted to ensure that all participants are included in the overall assessment, considering their compliance with the study protocol. The Last Observation

Carried Forward method will be used to input missing data values. A per-protocol analysis will also be conducted without participants who failed to complete at least 50% of the training sessions. Normality plots and Kolmogorov-Smirnov tests will be performed to test the normality of outcome variables. If normality is not satisfied, non-parametric tests will be applied (e.g., Krustal-Wallis). Mediators of change (i.e., mechanisms by which RDI) will be explored using structural equation modeling (AMOS 18.0) and multiple mediation analysis (PROCESS macro for SPSS). Putative candidates will include treatment (e.g., dose planned vs. given dose, planned cycles minimum/maximum, treatment interruption ratios, response to treatment, percentage of participants who needed dose adjustments, and the mean value of dose adjustment), and physiological (e.g., body composition, functional performance, handgrip strength, PA levels) variables. Mediation occurs when a causal effect of an independent variable occurs on a dependent variable, partly or entirely explained by a mediator. Indirect effects testing will be performed using Preacher and Hayes' procedures.

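### The protocol does not fix which result decides Hypothesis 1: the form of the outcome, the model term and the analysis set are all left open

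*Protocol*

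**What the plan says.** Objectives in the Protocol states Hypothesis 1 as one directional claim, with no metric: "Women in the intervention will have a better completion rate than those in the control group".

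The Primary outcome section gives completion two forms. One is continuous: "This outcome will be reported as the mean RDI". The other is a threshold: "A successful chemotherapy completion rate will be considered if the RDI is" at least 85% of plan. Assessment is at T0, T1 and T2, and no visit is named as decisive.

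Statistical methods applies one model family to everything: "Factorial ANCOVAs with repeated measures will be used for the primary and secondary outcomes". It adds "Independent sample T-tests will be used to compare results between groups at each time point", in a sentence that goes on to mention completers and non-completers, and a Fisher test on the proportion needing chemotherapy adjustments. It announces an intention-to-treat analysis and then: "A per-protocol analysis will also be conducted without participants who failed to complete at least 50% of the training sessions". If normality fails, non-parametric tests replace the planned ones. No analysis is ranked above another.

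Sample size says "sample size calculations were made for the primary outcome with a factorial variance analysis with repeated measures as reference statistical analysis", giving 82 before dropout at alpha 0.05 and power 0.80. It does not name the effect tested.

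Plans to promote retention, in a different section, removes low attenders and women who miss assessments from the data analysis.

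**The concern.** A superiority claim needs one result that settles it. Here a reader cannot tell which result that is. A repeated-measures factorial model returns at least two candidates, the group main effect and the group-by-time interaction, and the outcome definition supplies a second scale.

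The candidates answer different questions. By the Outcomes section, T0 falls one to two weeks after chemotherapy starts. By Sequence generation, allocation follows all baseline assessments. T0 RDI is therefore a pre-intervention value. The main effect averages it in; the interaction asks whether the between-arm difference changes from it.

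At stake is the meaning of a positive or negative trial. Two of these results can point in different directions in the same data, and the one presented as primary could be picked after the results are known.

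**Working it through.** **1. What the plan's own figure implies.** For the group main effect in a repeated-measures ANOVA with m measurements and correlation ρ, the noncentrality is λ = f² × N × m / [1 + (m − 1)ρ], on 1 and N − 2 degrees of freedom. The protocol says only that the effect is moderate. I assume f = 0.25 (d = 0.5) and ρ = 0.5.
- m = 4, N = 82: λ = 0.0625 × 82 × 4 / 2.5 = 8.2, power 0.808. This reproduces 82.
- m = 3, N = 82: λ = 0.0625 × 82 × 3 / 2 = 7.69, power 0.782; 80% power needs N = 86.
- Under the same assumptions the interaction needs only 28 (three visits) or 24 (four visits).

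So 82 fits a main effect with four measurements, whereas RDI has three. That hints that a main effect was intended but does not state it.

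**2. Why the two terms differ.** Let the true between-arm RDI difference be 0 at T0 (before allocation), δ₁ at T1 and δ₂ at T2. The main effect estimates (0 + δ₁ + δ₂)/3, which is 2δ/3 when δ₁ = δ₂ = δ. The interaction tests whether 0, δ₁ and δ₂ are equal. A chance imbalance at T0 moves the main effect but is not an intervention effect.

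**3. Why the two forms differ.** With assumed RDI means of 92 and 88, SD 8, values capped at 100 and 41 per arm, mean RDI is significant in 59% of simulated trials and the 85% proportion in 30%. The two disagree in 33%.

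**4. Two-sided error under no effect, if any one of several results could be claimed at 0.05.** Two settings were simulated. Setting A has 41 per arm and three equally correlated normal values (correlation 0.3-0.8). Setting B has T1-T2 correlation 0.5-0.9, skewed or normal RDI and 41-61 per arm. Neither adjusts for covariates, and none of these correlations is in the protocol.

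| Results that could be claimed (intention-to-treat) | Setting A | Setting B |
|---|---|---|
| Main effect or interaction | 9.6-10.9% | 6.5-8.2% |
| Those two plus t-tests at T1 and T2 | not run | 7.7-11.1% |
| Those four plus Fisher on RDI ≥ 85% and on adjustments | 15-18% | 11.4-14.9% |

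For comparison, two independent tests give 1 − 0.95² = 9.75% and six give 1 − 0.95⁶ = 26.5%. The simulated six-test values are lower because the tests are correlated.

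**5. Favourable direction only (Setting B).** Hypothesis 1 is directional, so a false claim of better completion requires a result favouring exercise. That error is 5.9-7.7% for the six intention-to-treat tests and 8.6-10.9% when the same six are repeated per protocol (10-20% excluded). Against 0.05 this is 5.9/5 = 1.2 to 10.9/5 = 2.2 times.

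**6. One prespecified contrast.** In Setting B the main effect alone gives 4.5-5.2% and the T2 t-test alone 4.8-5.4%, which is nominal.

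**7. Power of a single between-arm comparison.** With one value per woman, λ = 0.0625 × 82 = 5.125 and power is 61%. Reaching 80% needs 128 analysed (λ = 8.0). If covariates explain a share R² of the variance, λ becomes 5.125/(1 − R²): R² = 0.2 gives 6.41 and about 71%; R² = 0.4 gives 8.54 and about 82%. The protocol gives no R².

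**The case against.** The protocol does point to a lead analysis. The outcome is to be reported as mean RDI, Statistical methods opens with the repeated-measures model, Sample size names the same family, intention-to-treat comes first, and the per-protocol analysis is introduced as an addition. No between-arm test of the 85% proportion is written out, and the t-test sentence may compare completers with non-completers instead of arms. Hierarchies and alpha rules are often left to a statistical analysis plan, which is not shown here.

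Most of this stands, and it limits the size of the problem. It does not remove it. A lead model family is not a deciding term, and the two terms differ for the reason in step 2. Two forms of the primary outcome and conflicting rules on who is analysed are things this protocol itself states, so they are not details deferred to a later plan.

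A reader might infer two stronger things. The first is that every listed test competes at 0.05 and any significant one would confirm Hypothesis 1. The protocol does not say so: alpha appears only in Sample size, and the six-test count includes an unwritten test on the 85% cut and takes the t-tests as comparing arms. The second is that the chance of a false claim of better completion is two to four times the stated alpha. Multiples that large come from counting results in both directions, or from comparing with 0.025, which the protocol never states. In the favourable direction the figure is 1.2-2.2 times 0.05.

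The objection that a single contrast costs power is also right; the fix says so.

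**Conclusion.** The point holds in a limited form. The decision on Hypothesis 1 is badly fixed: two forms of the outcome, an unnamed model term, unranked companion tests, and an intention-to-treat statement that the retention section contradicts.

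The conditional two-sided error is about 6.5-11% if either model term could be claimed and about 11-18% if any of the six intention-to-treat tests could be. These ranges are not properties of the written plan. They assume that the deciding result is chosen after the data are seen, and they rest on assumed correlations and RDI distributions. The narrowest reading stays close to nominal: a T2 mean comparison plus the 85% cut gives 5.9-7.3% in Setting B.

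The missing decision rule itself is certain from the text, and it should be corrected before outcome data are examined.

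**What to change.** In Primary outcome, state that mean RDI over the whole course, computed with the section's own total-dose formula, is the primary form, and that the proportion reaching 85% is secondary.

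In Statistical methods, add: Hypothesis 1 is decided by one contrast, the covariate-adjusted between-arm difference in mean whole-course RDI in all randomised women, at two-sided alpha 0.05. The proportion with RDI of at least 85% is a secondary analysis. The group-by-time term, per-visit tests, dose-adjustment proportion and per-protocol analysis are supportive and cannot by themselves confirm Hypothesis 1. List the adjustment covariates instead of giving examples, and say whether the t-tests compare arms.

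Reconcile the exclusions in Plans to promote retention with the intention-to-treat set, so that they apply only to the per-protocol analysis.

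In Sample size, restate power for this contrast and do not carry over 0.80 from the repeated-measures calculation. With 82 analysed and d = 0.5, power is about 61% unadjusted; any gain from covariates needs a stated assumption.

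The cost is a few sentences and a new power statement. Two downsides should be disclosed: a positive result on a supportive analysis alone no longer confirms Hypothesis 1, and the restated power may fall short of 0.80 at the planned size.

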## **Trial design**

This study will be a 2-arm pragmatic and superiority randomized controlled trial with an intervention and an active control group, with a 1:1 allocation ratio. It will comprise a structured, supervised, home-based combined exercise intervention that will start 1-2 weeks after chemotherapy treatments begin and continue until 3-4 weeks post-treatment. Additionally, a 3-month follow-up will be performed. This protocol followed the Spirit guidelines.

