### **Outcomes**

Assessments will be performed at four-time points: baseline ( $T_0$ , 1-2 weeks post-chemotherapy start), mid-treatment ( $T_1$ , planned mid-cycle), post-intervention ( $T_2$ , 3-4 weeks post-chemotherapy finishing), and 3 months post-intervention finishing ( $T_3$ , follow-up). The primary outcome of this study will be the chemotherapy completion rates. Secondary outcomes will include functional performance, body composition, PA levels, sedentary behavior (SB) (i.e., behaviors with energy expenditure  $\leq 1.5$  METs while sitting, or lying ), and quality of life. Demographical information (age, education level, marital status, socioeconomic status), PA history, and clinical history data (disease and treatment history, concomitant comorbidities, and other existing health problems besides BC) will also be collected as covariates in the data analysis.

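### The supplementary t-tests are split by completion status, which is the primary outcome cut at 85%, and the Fisher test does not name the arms, so no listed test compares arms on the success criterion.

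*Protocol*

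**What the plan says.** **The outcome and hypothesis.** The Outcomes section states: "The primary outcome of this study will be the chemotherapy completion rates". The Primary outcome section sets the scale, "This outcome will be reported as the mean RDI", and adds a threshold: "A successful chemotherapy completion rate will be considered if the RDI is" at least 85% of the planned treatment. The protocol gives no other definition of completion. The Objectives frame the question as a contrast between arms: "Hypothesis 1: Women in the intervention will have a better completion rate than those in the control group". The Trial design section describes two arms, "with an intervention and an active control group, with a 1:1 allocation ratio".

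**The analyses.** Statistical methods list three tests that bear on this outcome:

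1. "Factorial ANCOVAs with repeated measures will be used for the primary and secondary outcomes", with covariate adjustment.
2. "Independent sample T-tests will be used to compare results between groups at each time point, considering chemotherapy completers versus non-completers".
3. A Fisher's test: "exact test will compare the proportion of participants who needed chemotherapy adjustments from those who did not".

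The second and third sentences name neither the intervention arm nor the control arm. Both cite an earlier trial of exercise during chemotherapy.

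**The concern.** Completion status becomes known after randomisation and is computed from the primary outcome. A t-test organised around it has two possible meanings, and neither estimates the effect of assignment. If the two groups are completers and non-completers, randomisation plays no part. If the groups are the arms, compared inside each completion stratum, the analysis selects women on the outcome that the intervention is meant to change.

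The Fisher sentence sets women who needed adjustments against women who did not. Taken literally, that is one proportion against its complement, with no second factor. Even with the arms added, needing an adjustment is a different endpoint from reaching 85%: a woman can have a dose changed and still finish above the threshold.

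Two misreadings of the results could follow. A highly significant difference between completers and non-completers could be presented as if it bore on exercise. Or a shrunken within-stratum difference could be read as no effect.

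**Working it through.** The protocol gives no RDI mean, SD or completion rate, so there is no stated figure to reproduce for this point. All RDI inputs below are assumptions. The 85% cut, the two arms and the 1:1 ratio come from the protocol.

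**Reading A: completers against non-completers.** This was simulated with RDI mean 90, SD 10, capped at 100, 41 women per arm (half of the 82 in Sample size) and 4,000 runs.

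- With no arm effect, the t-test of RDI between completers and non-completers rejects in 100% of runs, with a mean difference of about 15.3 points. A t-test between arms rejects in 4.7%, close to the nominal 5%.
- With the intervention arm shifted by 5 points before the cap, the true arm difference is about 3.8 points. The completer/non-completer difference moves only from 15.3 to 15.8.

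So this contrast carries almost no information about the arms.

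**Reading B: arms compared within each stratum.** For a normal RDI with mean m and SD s, put a = (0.85 - m)/s. Then

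- mean among completers = m + s·φ(a)/[1 - Φ(a)]
- mean among non-completers = m - s·φ(a)/Φ(a)

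The intervention mean is m + 0.5s. The fraction retained is the within-stratum arm difference divided by 0.5s.

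Worked case, m = 0.88 and s = 0.10, true difference 0.050:

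- Completers: 0.9668 - 0.9417 = 0.0250 (from unrounded means), and 0.0250/0.050 = 50%.
- Non-completers: 0.7933 - 0.7802 = 0.0131, and 0.0131/0.050 = 26%.

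| SD | Control mean | Retained, completers | Retained, non-completers |
|---|---|---|---|
| 0.10 | 0.85 | 42% | 31% |
| 0.10 | 0.88 | 50% | 26% |
| 0.10 | 0.92 | 62% | 21% |
| 0.12 | 0.85 | 42% | 31% |
| 0.12 | 0.88 | 49% | 27% |
| 0.12 | 0.92 | 58% | 22% |

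The normal model is uncapped. These inputs place 7-25% of control women and 16-43% of intervention women above 100% RDI. The capped simulation gives the same picture: the 3.8-point arm difference falls to about 1.6 among completers (1.61/3.83 = 42%), and power falls from 0.56 to 0.25.

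**Other outcomes under reading B.** Take an outcome correlated 0.1-0.3 with RDI, with a 0.5 SD effect on both, control RDI mean 0.88 and SD 0.10. Then 85-95% of its effect is retained among completers and 78-93% among non-completers. The distortion is much smaller there.

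**An arm comparison on the 85% criterion.** With a two-sided alpha of 0.05, the normal approximation and assumed completion rates:

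| Control vs intervention | 41 per arm | 49 per arm | 61 per arm |
|---|---|---|---|
| 70% vs 85% | 0.37 | 0.43 | 0.51 |
| 70% vs 90% | 0.62 | 0.70 | 0.80 |

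The sizes are half of 82 and 98 (Sample size) and of 122 (Abstract). Fisher's exact test would have somewhat less power. At these sizes the binary test suits a supportive role.

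**The case against.** The strongest reply is that the plan already holds the needed analysis. The ANCOVA is assigned to the primary outcome, that outcome is reported as mean RDI, the sample size rests on the same type of model, and an intention-to-treat analysis is stated. In a two-arm trial the between-subject factor is naturally the arm. This stands. A reader might infer that the plan has no randomised comparison of the primary outcome, or cannot address Hypothesis 1 at all. The documents do not support that.

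The Fisher sentence is also probably loose grammar. The test needs a second factor, and arm is the only plausible one. An arm-by-adjustment table is a valid analysis, so this part is a wording fault, not a wrong choice of test.

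The t-test sentence is ambiguous too. Its groups may be the arms, and its results may include secondary outcomes, for which an association with completion is a legitimate exploratory question. But the ambiguity does not rescue it as a test of the intervention, because both readings depend on a post-randomisation split.

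Finally, a responder test on the 85% threshold could be left to a statistical analysis plan. That would be fair if the protocol were silent. Here it specifies tests around completion and gives them the wrong contrast or none, so a later plan would have to depart from it. The citation of an earlier trial does not change what the split does in this one.

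**Conclusion.** The point holds within limits. The t-tests as worded do not estimate the randomised effect, on either reading. The Fisher sentence needs its comparison groups named. No listed test compares arms on the RDI threshold that the completion rate in Hypothesis 1 implies. The ANCOVA on mean RDI is unaffected.

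The structural fault needs no numerical assumption. The size does: 42-62% retained among completers and 21-31% among non-completers applies to RDI within strata only, under an assumed uncapped normal distribution, control mean 0.85-0.92, SD 0.10-0.12 and a 0.5 SD effect. It should not be read as the bias in the trial's main result, nor carried over to secondary outcomes weakly correlated with RDI.

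The change should be made, because it alters what the listed tests estimate and costs almost nothing.

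**What to change.** In Statistical methods:

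1. Delete the closing clause of the t-test sentence that brings in completion status, and state that the t-tests compare intervention with control in all randomised women.
2. State that Fisher's exact test compares the two arms on the proportion with RDI of at least 85% at T2 and, separately, on the proportion needing any dose adjustment.
3. Label the t-tests and Fisher's tests as supportive of the ANCOVA on mean RDI.
4. Keep any table of completers and non-completers descriptive, without a test presented as an effect of the intervention.

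The cost is a rewrite of two sentences. No extra data, visits or participants are needed, since RDI and dose changes already come from the medical records.

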### **Interventions**

**Combined home-based exercise group.** Participants in this group will exercise throughout their chemotherapy treatments, starting within 1-2 weeks of its start and ending within 3-4 weeks post-treatment completion .

The exercise intervention will be led by qualified exercise professionals, comprising two weekly 60-minute online exercise group sessions with a 5-minute warm-

up, a 30-minute resistance training, and a 20-minute aerobic exercise component, finishing with a 5-minute cooldown . The warm-up will be composed of mobility and activation movements, such as cat-camels, butterfly chest stretch, overhead reach, floor angels, spine twist in sitting and alternated all fours position, doorway chest stretch, wall slides, scissors, pointer, and single leg stances. The resistance training component will consist of 9 different exercises, performed either with body weight or free weights, completing 2-3 sets of 10-15 repetitions, and will involve movements such as chair sit-to-stand, multi-directional lunges, calf, and toe raises, double-arm and one-arm rows, push-ups, glute bridges, clams, chest press, multi-directional shoulder raises, leg curls, and abdominal exercises (i.e., crunches, leg raises, crisscross) . The aerobic component will consist of low-impact dance exercises, moving large muscle groups to increase heart rate, involving marching, side steps, knee raises, leg curls, multi-directional arm movements, and dance movements . The cooldown will consist of breathing exercises and light stretches. Every exercise professional will follow a written protocol to ensure consistency in the intervention program's application .

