## **Data collection, management, and analysis**

### **Data collection methods**

Assessments will be conducted in standardized conditions, in a clinical setting, in a calm and comfortable environment, in small groups, and performed by a qualified exercise professional. The assessments will be conducted in the morning, starting with the body composition measurements, followed by a 15-minute pause so participants can eat (since they will be weighted while fasting), preceded by a 10-minute warm-up with general movements to mobilize big muscle groups and the physical tests, that will be performed in the following order: shoulder angular measurements, strength, mobility, and aerobic endurance. Participants will be divided into small groups to facilitate instruction and conduction of the tests. Participants will receive the accelerometers one week before

the field tests and return them on the physical assessment day. After the field measurements, all questionnaires will be delivered and answered through email (Google Forms). Summarized information regarding assessment time points and tools can be found in Table 1.

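### Last observation carried forward can enter program-period activity as 3-month activity, so the Hypothesis 3 comparison may partly assume the persistence it is meant to test

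*Protocol*

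**What the plan says.** - **Missing data.** Statistical methods: the Last Observation "Carried Forward method will be used to input missing data values". No outcome or visit is exempted, and no other method or missing-data sensitivity analysis is named.
- **What T3 is for.** Objectives: "A 3-month follow-up will be performed to investigate short-term outcomes and active lifestyle sustainability post-intervention". Hypothesis 3 reads: "In the post-intervention period, women in the intervention group will maintain a more physically active lifestyle than women in the control group".
- **End of the program.** Interventions: women exercise during chemotherapy, "starting within 1-2 weeks of its start and ending within 3-4 weeks post-treatment completion".
- **Timing of T2.** Outcomes: T2 is placed at "3-4 weeks post-chemotherapy finishing", and T3 three months after the intervention ends.
- **Activity measurement.** Data collection methods: "Participants will receive the accelerometers one week before" the field tests. The Physical Activity section sets seven days of wear.
- **Rules that remove data.** Under Blinding, everything recorded after a woman leaves is set aside. Under Plans to promote retention, women who miss assessments in the intervention period are dropped from the analysis. Statistical methods nevertheless announces an intention-to-treat analysis of all participants.

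**The concern.** Hypothesis 3 asks whether exercise-arm women stay more active once supervision stops. Program end and T2 share a window, and the accelerometer is worn in the week before the T2 tests. The T2 activity value may therefore describe a week in which the exercise arm was still offered two 60-minute exercise sessions and encouraged to walk, while controls had one 30-minute session of breathing, stretching and relaxation. If a woman then misses T3, LOCF records that week as her activity three months later. For her, persistence has been assumed, not observed. Enough such women in the exercise arm could yield an apparent sustained benefit when no behaviour was sustained.

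A second problem concerns outcomes that chemotherapy is expected to worsen. The Introduction says that its side effects hinder functional performance. If early leavers are kept in the intention-to-treat analysis, LOCF gives them their T0 function and quality-of-life scores at every later visit, so leaving is scored as no decline.

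**Working it through.** **1. Inputs.** The protocol gives no figure for the effect of missing data. Its only attrition figure is the 20% dropout in Sample size: 82 x 1.20 = 98.4, stated as 98, or 49 per arm at 1:1. The abstract's recruitment goal of 122 would give 61 per arm. Both sizes are used below. The T2 group difference, the correlation between visits, and the timing and balance of losses are not given, so they are assumptions.

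**2. What LOCF carries to T3.**

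| Last visit attended | Value carried | Status of that value |
|---|---|---|
| T2 | T2 | Program period, if the wear week precedes the last session |
| T1 | T1 | Program period (mid-treatment) |
| T0 | T0 | Before allocation, so no expected arm difference |

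If the exclusion under Plans to promote retention is applied, the second and third rows largely drop out and the first remains. If the intention-to-treat sentence prevails, all three occur.

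**3. Expected T3 difference.** Let d be the share in each arm with T2 carried to T3, and D2 and D3 the true arm differences at T2 and T3. With equal losses and no common change in activity between visits:

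expected LOCF difference = (1 - d) x D3 + d x D2

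With D3 = 0 this is d x D2, in SD units:

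| d | D2 = 0.3 | D2 = 0.5 | D2 = 0.8 |
|---|---|---|---|
| 10% | 0.03 | 0.05 | 0.08 |
| 20% | 0.06 | 0.10 | 0.16 |
| 30% | 0.09 | 0.15 | 0.24 |

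**4. False positives and timing of loss.** Simulation: 10,000 runs, correlation 0.5, two-sided t-test at T3, true T3 difference zero. Each cell gives the mean difference in SD and the rejection rate at nominal 5%.

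| Per arm | Share lost | D2 | All carry T2 | Half carry T0 | All carry T0 |
|---|---|---|---|---|---|
| 49 | 20% | 0.5 | 0.10; 7.4% | 0.05; 5.6% | about 0; 5.2% |
| 49 | 20% | 0.8 | 0.16; 11.2% | 0.08; 6.4% | about 0; 5.0% |
| 49 | 30% | 0.8 | 0.24; 20.2% | 0.11; 8.1% | about 0; 4.8% |
| 61 | 20% | 0.5 | 0.10; 8.0% | 0.05; 5.9% | about 0; 5.2% |

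The simulation error at 5% is the square root of 0.05 x 0.95 / 10,000, about 0.2 percentage points. The last column is therefore compatible with 5%, and 7.4% is not.

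**5. Unequal loss.** Suppose activity falls by 0.5 SD between T2 and T3 in controls, the true T3 difference is zero, and D2 = 0.5. Take the control T2 mean as 0. The exercise T2 mean is then +0.5 and both T3 means are -0.5.

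- Loss 30% exercise, 10% control: exercise 0.3 x 0.5 + 0.7 x (-0.5) = -0.20; control 0.1 x 0 + 0.9 x (-0.5) = -0.45. Difference +0.25 (simulated +0.26, 21% false positives).
- Loss 10% exercise, 30% control: exercise 0.1 x 0.5 + 0.9 x (-0.5) = -0.40; control 0.3 x 0 + 0.7 x (-0.5) = -0.35. Difference -0.05 (simulated about -0.05, 5.0%).

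The sign therefore depends on which arm loses more women and on what is carried.

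**The case against.** **The overlap is possible, not certain.** Program end and T2 are both 3-4 week windows, and T2 is labelled post-intervention. If sessions stop at week 3 and the tests are at week 4, the wear week falls after the program. This stands, so the point is that the T2 value can be on-program. The protocol does nothing to prevent it.

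**The bias need not favour exercise.** A reader might infer that LOCF always helps the exercise arm. The working shows otherwise: the bias fades as more T0 values are carried and can turn slightly negative with unequal loss.

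**The retention exclusion may remove early leavers.** If it is applied, no one carries T0 function or quality-of-life scores. The no-decline problem therefore depends on the intention-to-treat sentence prevailing, and the protocol does not say which rule governs.

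**The primary outcome is less exposed than it looks.** One might infer that RDI carried from T0 is near 100% by construction. The documents do not say so, and RDI comes from medical records, so a missed visit need not make it missing. It would be lost mainly through the rule that sets aside data after a woman leaves.

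**Standard errors.** One might add that LOCF makes them too small. That has not been shown here: with no shift in means, rejection stays at about 5%.

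**Size.** The 20% is overall dropout, stated for a primary outcome last assessed at T2. It is not a forecast of women seen at T2 and missing at T3, and monthly contact is planned to keep women for T3. Converting session lengths into minutes per week of activity difference would also treat every session minute as measured activity, which the documents do not support. SD units with a stated range are safer.

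**Conclusion.** The point holds in a conditional form. The protocol fixes LOCF for all missing values, and its own timing allows program-period activity to be entered as activity three months after the program. When T2 values are carried, losses are similar and the true T3 difference is zero, the spurious difference is the carried share times the T2 difference. The central illustration (20%, 0.5 SD, 49 per arm) gives 0.10 SD and about 7% false positives. Over 10-30% carried and 0.3-0.8 SD at T2, the spurious difference runs from 0.03 to 0.24 SD. These sizes rest on assumed T2 differences, a correlation of 0.5 and a simple T3 t-test, so they show scale and do not predict the result. The function and quality-of-life problem holds only if intention-to-treat overrides the retention exclusion. Hypothesis 3 is secondary, so this does not undermine the trial, but it should be changed before analysis.

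**What to change.** In Statistical methods, replace LOCF with a linear mixed model for repeated measures on all observed values, with terms for arm, visit, arm-by-visit, baseline and the covariates already named there, and no single imputation. This estimates the change from T2 to T3 instead of setting it to zero.

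The model still assumes that missing values can be predicted from the data observed. For T3 activity, therefore, add one sensitivity analysis that imputes missing exercise-arm values from the control arm's T3 distribution. This asks whether a finding of sustained activity survives if the women not seen resemble controls.

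Take RDI from the medical records instead of carrying it forward. Reconcile the rules under Blinding and Plans to promote retention with the intention-to-treat statement. Otherwise data already collected would still be discarded, and changing the model alone would not recover them.

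The cost is a revision of the text, somewhat wider intervals and slightly more analysis work. The named SPSS version fits mixed models and multiple imputation. Sample size cites a repeated-measures analysis of variance as its reference, so a sentence there should note the changed model. No extra visits or measurements are needed.
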